Economic evaluation methods will include document reviews and exit interviews with individuals accessing HIV testing services.

In the **two secondary distribution models**, the study will explore factors associated with successful secondary distribution of test kits. Specific objectives are to measure:

9. Factors associated with acceptance of HIVST for secondary distribution to index patients, acceptance being evidenced by accepting an HIVST kit(s) for onward secondary distribution.
10. Factors associated with the successful secondary distribution of HIVST to the sexual partners (the intended users of the secondary distribution HIVST kits) of index patients, as evidenced by the proportion of index patients who report that their primary partners used the HIVST kit within 1 month of distribution
11. The proportion of intended users of the secondary distribution HIVST kit who report having accessed confirmatory testing, or HIV prevention or care services within 3 months of distribution
12. User experiences and factors affecting the potential for social harms

To meet these objectives, we will administer a quantitative exit interview after the clinical consultation to determine the proportion of individuals who accepted an offer of an HIVST for secondary distribution and factors associated with acceptability of an offer of a secondary distribution HIVST (objective 9). For individuals who accepted the offer of a secondary distribution HIVST, we will conduct a follow-up questionnaire approximately 1-month after the initial exit interview to measure use of the HIVST kit (objective 10) and will follow-up their partner approximately 3-months after distribution to measure linkage to confirmatory testing, HIV care or prevention services (objective 11). To complement the quantitative data, a purposive sample of individuals participating in the exit interview will be followed-up at three-time points as part of a qualitative cohort, with IDI conducted each time point to understand

user experiences, factors influencing secondary distribution of an HIVST, and social harms (objective 12).

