### **2.2 Study objectives**

For each of the five distribution models, the specific objectives are to use routinely collect programmatic data and qualitative data from the case studies to:

1. Describe, quantitatively, the process of distributing HIVST kits through each of the five distribution models;
2. Understand individuals' experiences of the different models of HIVST distribution;
3. Explore contextual factors likely to influence the acceptability of different models of HIVST to direct and secondary-distribution kit recipients. For example, at community level we will explore how availability of alternative HTS, anticipated and enacted stigma, and location of the distribution models influence people's choices. At interpersonal level, we will explore how power dynamics within a couple influence individuals' decisions.

4. Evaluate the frequency and nature of social harms associated with distribution of HIVST kits, and
5. Develop generalizable qualitative tools that can be used to evaluate different distribution models among key target populations

For four of the five models (all models except VMMC) we will also measure:

6. Costs, from the patient and the provider-perspective, of accessing and delivering HIVST kits, and those relating to linkage into confirmatory testing and care for individuals who self-test HIV-positive
7. The incremental cost-effectiveness of additional HIVST distribution models
8. Patient costs and their willingness-to-pay for HIVST

For the two secondary distribution models (implemented in ANC and HIV testing and treatment services), we will recruit a cohort (Secondary Distribution cohort) of index patients and their sexual partners (intended users of the HIVST kit) in order to investigate:

9. Factors associated with acceptance of HIVST for secondary distribution to index patients, with acceptance evidenced by accepting an HIVST kit(s) for onward secondary distribution.
10. Factors associated with the successful secondary distribution of HIVST to the sexual partners (the intended users of the secondary distribution HIVST kits) of index patients, as evidenced by the proportion of index patients who report that their primary partners used the HIVST kit within approximately 1-month of distribution
11. The proportion of intended users of the secondary distribution HIVST kit who report having accessed confirmatory testing, or HIV prevention or care services within approximately 3-months of distribution

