#### **4.3.2 Secondary Distribution Cohorts**

For the two secondary distribution models, we will recruit two cohorts of individuals (one from ANC and one from HIV+ individuals attending HIV testing and treatment services) to collect data on outcomes of distribution over time (Figure 2 and 3 First, we will conduct an exit interview with consecutive HIV+ individuals (attending HIV testing and treatment services) and ANC attendees (HIV status irrelevant) to determine the proportion who accepted an offer of an HIVST for secondary distribution and determine factors associated with accepting an offer of HIVST for secondary distribution.

At the end of the exit questionnaire, individuals self-reporting that they accepted an offer of secondary distribution HIVST will be asked for permission to be followed-up within 1-month after the exit interview to measure use of the secondary distribution HIVST. We will also aim to

follow-up the intended user of the secondary distribution HIVST within approximately 3-months to measure self-reported use and linkage to care as reported by the intended users. A timeline specific to the secondary distribution cohorts is given in Figure 2.

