**Figure 2: Schematic of the quantitative and qualitative cohort in ANC and ART models**

For the secondary distribution cohorts, we will measure individual- and couple-level factors associated with acceptability to the index patient and intended user including: sex, age, previous HIV testing history, newly diagnosed or previously undisclosed HIV, relationship of the distributor and intended user (including type of relationship, age differential, measures of equality and empowerment), history of gender based violence and clinic from which the Index was recruited (ANC or HIV testing and treatment services).

The primary outcome of the secondary distribution cohorts is the:

- 1) Proportion of index patients who accepted an offer of secondary distribution HIVST kit(s) who report that their sexual partner(s) used the HIVST kit,

Secondary outcomes are the:

- 1) Proportion of index patients accepting an offer of HIVST kit(s) for secondary distribution,
- 2) Proportion of index patients who accepted an offer of a secondary distribution HIVST kit(s) who report that their partner used the HIVST kit(s) and linked to prevention or care services within 1-month of distribution

- 3) Proportion of intended recipients who self-report a) having used an HIVST kit and b) having attended confirmatory HIV testing, or HIV prevention or HIV care services within 3-months of distribution.

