Approximately one-month after the offer of HIVST for secondary distribution, RAs will follow-up cohort participants who reported accepting an offer of an HIVST for secondary distribution, either at the health facility or in their homes or other convenient place. It is anticipated that a number of individuals who will accept the offer of HIVST secondary distribution may not return to the clinic on the appointment day for various reasons. Such individuals will be followed-up using a phone call or to their homes using the information provided during the exit interviews. A maximum of three (3) attempts on three different days through phone calls or home visit will be made. Individuals not answering the phone calls or not at home after three attempts will be considered lost-to-follow-up from the cohort.

To recruit the intended users of secondary distribution HIVST, individuals accepting a secondary distribution HIVST and who report that their partner (intended user) used the HIVST will be asked for permission to contact their partners, the intended users. For individuals who will give permission, the RA will either: (1) give the individual a card containing the RA’s contact details for the partner to call the RA or (2) ask the individual if they are willing to call their partner (intended user) to ask for permission to a) share their (intended user’s) phone number with the RA b) to introduce the RA to them (intended user). For intended users who will be willing to share their phone numbers or to talk to the RA, the RA will briefly introduce the study and obtain verbal permission. For intended users who will give verbal permission, the RA will obtain contact details and arrange to meet them. A maximum of three (3) attempts on three different days through phone calls will be made to contact or meet the intended user. RAs will arrange to meet the intended user at the clinic or at their home or any place provided it is safe and convenient for both the RA and the intended user. The intended user will also be provided with information about the study and asked to provide written consent before they are interviewed. The follow-up surveys for the distributor of the secondary distribution HIVST

and the intended user of the HIVST will focus on usage of the collected HIVST and linkage to care or HIV prevention services including their costs of accessing HIVST and linkage to HIV services as well as their willingness to pay for HIVST.

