### **7.3 Quantitative secondary distribution cohort data**

For the quantitative data arising from the secondary distribution cohorts, we will conduct analyses separately for the ANC and HIV testing and treatment cohorts. We will use descriptive analyses to describe the proportion of individuals accepting an offer of HIVST and the proportion who report that their partner used the HIVST. We will use standard logistic regression adjusting for study site to explore factors associated with accepting an offer of HIVST and with reported use of the HIVST.

Although the index individuals will be asked about linkage to care at 1-month follow-up, we will measure linkage to care using data from the intended users followed-up within 3-months after distribution. Linkage will be measured as the number of individuals reported to have linked to care (defined as accessing confirmatory testing services or attending an HIV care clinic for HIV-positive individuals or accessing VMMC services for HIV-negative males) among those who reported use of the HIVST.

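### The partner interview behind the 3-month linkage outcome has inconsistent timing and no earliest date, so some partners may be counted before 3 months have passed

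*Protocol*

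**What the plan says.** The protocol gives the timing of the partner (intended user) interview in three ways.

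- Summary, a point in time: "will follow-up their partner approximately 3-months after distribution to measure linkage to confirmatory testing, HIV care or prevention services".
- Section 4.3.2, an upper limit: "follow-up the intended user of the secondary distribution HIVST within approximately 3-months to measure self-reported use and linkage to care".
- Section 7.3, an upper limit: "we will measure linkage to care using data from the intended users followed-up within 3-months after distribution".

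The outcome is cumulative. Secondary outcome 3 in section 4.3.2 is the proportion of intended recipients who report use and "having attended confirmatory HIV testing, or HIV prevention or HIV care services within 3-months of distribution". Objective 11 in section 2.2 is slightly looser: "confirmatory testing, or HIV prevention or care services within approximately 3-months of distribution".

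Section 5 makes a partner eligible only if the index patient consents at their own follow-up interview. Section 5.2 places that interview early: "Approximately one-month after the offer of HIVST for secondary distribution, RAs will follow-up cohort participants". For partners who then agree, "the RA will obtain contact details and arrange to meet them". At most three contact attempts are allowed. No waiting period, earliest date or repeat contact is stated.

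Section 7.3 defines linkage as the number reported to have linked among those who reported using the kit.

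**The concern.** A proportion linked within 3 months requires each partner to be observed for 3 months. A rule that sets only a latest date does not secure this. Read literally, section 7.3 admits interviews that cannot see the whole window and leaves out those held just after it closes. A partner met at 5 weeks who goes for confirmatory testing at 8 weeks would be recorded as not linked and would not be contacted again.

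This interview is the source that section 7.3 names for linkage. Section 4.4.2 uses service use reported in the cohort to cost linkage. Appendix 1 states that the secondary distribution models have no individual tracking of linkage. Little else could correct a figure whose time label is wrong.

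**Working it through.** **Is an early interview allowed?** Partner contact opens at about 1 month (sections 5 and 5.2). The latest date is 3 months (section 7.3) or about 3 months (section 4.3.2). Neither these sections nor section 5.2 gives an earliest date, so an interview at 5 to 8 weeks complies with all three and conflicts only with the Summary. The timeline in section 9.3 lists follow-up of cohort participants and intended users as one activity. Figure 3 gives the two interviews separate rows, but its timing bars are not readable in the text at hand, and Figure 2 is not shown.

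**Can the analysis repair it?** Only in part. The tools record the interview date (PS 1), the kit collection date (Use_HIVST 1), the month of registration for HIV care (Link_HIV_Care 4) and the ART start date. The intended-user questionnaire has no date for confirmatory testing (Link_HIV_Care 1) or for clinic attendance after a non-reactive test (Link_HIV_Care 13). Confirmatory testing is a named part of linkage, so that part cannot be cut at 3 months or analysed by event date afterwards.

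**Direction.** Let F(t) be the proportion linked by t months after distribution. F cannot fall as t rises, so F(t) ≤ F(3) for any interview at t < 3. Taken alone, early timing can only lower the estimate.

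**Size.** The protocol states no linkage rate, so there is no figure to reproduce. The sample size in section 5.4 concerns reported use at 1 month and is unaffected. The values of F(3) below, the curve shapes and the even spread of interviews are all assumptions.

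- Constant hazard: h = −ln(1 − F(3))/3 and F(t) = 1 − exp(−ht). The average over interviews spread evenly from month 1 to month 3 is 1 − [exp(−h) − exp(−3h)]/(2h).
- Example, F(3) = 50%: h = 0.6931/3 = 0.2310. F(1) = 1 − exp(−0.2310) = 20.6%. Average = 1 − (0.7937 − 0.5)/0.4621 = 36.4%.
- Front-loaded linkage (Weibull, shape 0.5): F(t) = 1 − exp(−c√t) with c = −ln(1 − F(3))/√3, averaged numerically.

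| Assumed F(3) | Curve | All at 1 month | All at 2 months | Even over months 1–3 | Shortfall, even spread (points) |
|---|---|---|---|---|---|
| 30% | constant | 11.2% | 21.2% | 21.0% | 9.0 |
| 50% | constant | 20.6% | 37.0% | 36.4% | 13.6 |
| 80% | constant | 41.5% | 65.8% | 64.1% | 15.9 |
| 30% | front-loaded | 18.6% | 25.3% | 25.0% | 5.0 |
| 50% | front-loaded | 33.0% | 43.2% | 42.7% | 7.3 |

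With an even spread the shortfall is about 5 to 16 points. In the extreme case with every interview at 1 month, it runs from 30 − 18.6 = 11.4 to 80 − 41.5 = 38.5 points. If all partners are seen at about 3 months, it is close to zero.

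**The case against.** The best defence is that the protocol uses the word within loosely. The index visit is put within 1 month in sections 4.3.2 and 5.2, yet at about 1 month in the Summary and elsewhere in section 5.2, and nobody would read that as a visit at any time from day 0. Section 7.3 also contrasts index reports at 1 month with partner data at 3 months, which would have little point if both were collected together. Figures 2 and 3 may show the intended schedule. Linkage is a descriptive outcome (section 5.4), section 7.4 plans to describe time to linkage, and handling unequal follow-up is ordinary SAP content.

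Much of this stands. It makes an intended interview at about 3 months plausible, and it rules out three stronger readings that a reader might infer.

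- *Partners are scheduled at 1 month.* No passage says so. Section 5.2 merely fails to prevent it.
- *Reported linkage is biased low overall.* Only the timing effect has a known sign. Partners are interviewed only if the index patient reports use and permits contact, and the partner consents. That selection could plausibly push linkage upward.
- *Comparisons between sites or between the two cohorts are distorted.* No such comparison of linkage is planned. Section 7.3 analyses the cohorts separately and uses regression only for acceptance and reported use.

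The timing argument also barely touches the use part of secondary outcome 3, since partners are approached only after use has been reported.

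The defence does not remove the conflict in the text. Field staff work from section 5.2, which has no earliest date, and an SAP cannot recover event dates that the questionnaire never asks for.

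**Conclusion.** The point holds as an inconsistency in timing that should be settled before partner interviews begin. The Summary gives one time point, sections 4.3.2 and 7.3 give only upper limits, and section 5.2 allows a meeting from about 1 month. Some partners may therefore be interviewed early and still counted in a within-3-months proportion.

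The timing effect can only be downward. Its size is unknown: the 5 to 16 points rest on assumed linkage of 30% to 80%, two assumed curve shapes and an assumed even spread of interviews. At the Summary's timing it would be near zero. The net direction of bias is not established. The consequence is limited to a descriptive secondary outcome and the linkage costing that draws on cohort data.

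**What to change.** - Keep the 1-month index visit for permission and partner contact details.
- In sections 4.3.2, 5.2 and 7.3, in line with the Summary, state that the partner interview is held at, and not before, about 3 months after distribution.
- Add dates to the intended-user questionnaire for confirmatory testing and for clinic attendance after a non-reactive test. Linkage can then be counted to 3 months by event date, and any earlier interview treated as censored.

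A fixed window such as day 90 to 120, and a phone call at 3 months to partners who could be met only earlier, are optional.

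The cost is protocol wording, interview scheduling and a few questionnaire items. Appendix 3 already says that its response options, order and skip patterns may change when programmed. The downside is somewhat more loss of partners between permission and interview, under a limit of three contact attempts.

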### **1.1 Background and rationale**

Over the past decade, the delivery of HIV testing services (HTS) across southern Africa has evolved from solely facility-based to delivery of HTS through community-based settings, including community-based campaigns, mobile vans, and the door-to-door offer of home-based HIV testing from lay counsellors.[5] In many sub-Saharan African countries, this scale-up of HTS has led to an increase in the proportion of individuals ever-testing for HIV and receiving the result of an HIV test, and has contributed to progress in reaching the first-90 of the UNAIDS 90-90-90 targets.[6-9] In 2016 in eastern and southern Africa, an estimated 76% of individuals living with HIV knew their HIV-positive status, among whom 79% were on anti-retroviral therapy (ART) treatment.[2, 8] In 2016 in Zambia, 70% of women and 63% of men knew their HIV-positive status.[10] A similar percentage (~85%) of men and women who knew their HIV-positive status self-reported ART treatment use.[10] Relative to 2010, there was a 4% decline in HIV incidence in 2015 in eastern and southern Africa.[11]

Despite progress in the region towards the UNAIDS 90-90-90 targets, HIV incidence remains high among a number of sub-populations and there are critical gaps along the treatment cascade, with a third of individuals living with HIV remaining undiagnosed.[2, 8] To improve all steps in the HIV care continuum and link more people into HIV prevention services, including voluntary medical male circumcision (VMMC) and oral pre-exposure prophylaxis (PrEP), there remains a need to improve access to HTS in order to facilitate linkage to HIV prevention, or treatment and care services.[11] Among the populations hardest to reach with HTS are men, adolescents and younger adults, and populations with higher levels of mobility.

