**Table 1: Summary of HIVST distribution models**

Model	Description	Implementer
1 VMMC	VMMC mobilizers distribute HIVST to men interested in VMMC.	SFH
2 Facility-led and Community-led	The facility-led model will utilize existing clinics to distribute HIVST kits within specified departments of the facility and during outreach programs.  HIVST kits will be distributed using existing community structures such as shops of hubs (kanterbas) that are otherwise not directly linked to the health facilities. Communities will determine the best way to distribute the tests and manage all distribution activities.	SFH Zambart and MOH  SFH and Zambart
3 Workplace	Distribution of HIVST in targeted workplaces where HIV risk may be high (uniform/security professionals, truck drivers, taxi ranks etc.) and testing using routine finger-prick test is low or unsuccessful, HIVST distribution through peer educators or distribution agents.  Distribution will be done in a private room or outside in a tent. Workers will walk in at their own time to collect an HIVST. Process data will be collected using a self-administered questionnaire. There will be no individual tracking for linkage to care and treatment.	SFH
4 Secondary Distribution through ANC	This model is part of the facility-led HIVST distribution model, above. HIVST for secondary distribution will be offered to women attending ANC for their primary partners.	SFH and MOH
5 Secondary distribution through individuals who know their HIV	Trained lay counsellors for Zambart models and SFH and MOH staff for models implemented by SFH will distribute HIVST through individual HIV+ patients. The lay counsellors will offer HIVST kits to HIV positive individuals who self-report to: be in a discordant	Zambart, MOH and SFH

---

positive status	relationship; to have a partner with unknown HIV positive status or to have HIV negative partner who wishes to re-test.
-----------------	---

---

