Use_HIVST 3	Did you give your partner an HIV self-test kit that you collected on his behalf?	No; Yes	0; 1
Use_HIVST 3a	If no, why did you not give the HIVST to your partner?	I lost the kit; my partner already knows his/her HIV positive status; I feared my partner would get angry; my partner has been away from the time I collected the test kit; my partner and I are no longer in partnership; other (Specify); refuse to respond	1; 2; 3; 4; 5; 6; 7
Use_HIVST 4	Did your partner use the HIV self-test that you gave him?	Yes – I was present when he used the self-test; Yes – I was told that the self-test kit was used; No- he did not use the self-test kit; I Don't know	1; 2; 3; 4
Use_HIVST 5	What was the date that your partner used	Year; month; day	

	the HIV self-test kit?		
Use_HIVST 6	When your partner used the self-test, did you also use a self-test at the same time?	Yes (Couple testing); No; Don't know	1; 2; 3
Use_HIVST 7	What were the results of your self-test?	HIV-positive; HIV-negative; Indeterminate; Don't know; Refused to answer	1; 2; 3; 4; 5; 6
Use_HIVST 8	Do you know the results of your partner's HIV test?	No; Yes; Don't know; Refused to answer	1; 2; 3; 5
Use_HIVST 9	What was your partner's test result?  Interviewer: Remind participant that they do not have to answer this question if uncomfortable. If she says that she knows but doesn't want to share – this is code 99. If the person tested but did not share the result with them so they don't know, this is code 98	HIV-positive; HIV-negative; Indeterminate; Don't know; Refused to answer	1; 2; 3; 4; 5
Use_HIVST 10	Did your partner go to a clinic or health facility in order to confirm the result that was obtained from the self-test (confirmatory testing)?	No; Yes; Don't know	0; 1; 2
Use_HIVST 11	Did your partner go to a clinic or health facility for HIV care?	No; Yes; Don't know	0; 1; 2
Use_HIVST 122	Is your partner currently in ART care?	No; Yes; Don't know	0; 1; 2
Use_HIVST 13	Did your partner go to the clinic or health facility for HIV prevention services?	No; Yes; Don't know	0; 1; 2
Use_HIVST 14	What HIV prevention services did they go for?	VMMC; to collect condoms; other (specify)	0; 1; 2

Social Harms/benefits Screening at follow-up visit			
Variable Name	Question	Options	Option Codes

SHS_Fu_1	When you gave your partner the HIV test kits, did you explain that it is for HIV testing?	Yes; No; Don't know	1; 2; 3

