H_HIV_Test_IU 3j	It's not a dignified thing to do at my age	No; Yes	0;1
H_HIV_Test_IU 3.10	It's not a dignified thing to do at my age	No; Yes	0;1
H_HIV_Test_IU 3.11	The health facilities offer poor quality services, including lack of confidentiality	No; Yes	0;1
H_HIV_Test_IU 3.12	I do not trust health providers	No; Yes	0;1
H_HIV_Test_IU 3.13	I do not feel sick enough	No; Yes	0;1
H_HIV_Test_IU 3.14	Other reason	Specify	
H_HIV_Test_IU 3.15	Of the reasons for not testing for HIV, what is the main reason you have not HIV-tested?	OPTIONS from selections picked	
H_HIV_Test_IU 4	When did you last test for HIV?	DDMMYYYY	
H_HIV_Test_IU 4	What was the result of your last HIV test?	Reactive/ positive; non-reactive/negative; I don't know; I can't disclose	1; 2; 3; 4
H_HIV_Test_IU 6	Over the past 12 months, during your relationship with your partner, do you	Yes – I know with another spouse;	1;2;3;4;5

	know or suspect that your partner was having sex with someone else?	Yes – I know with another partner or partners; Yes - I believe there was another partner or partners; No, I know this partner did not have other partners; Don't know/No answer	
H_HIV_Test_IU 7	If you consider your behavior (current or past) with respect to getting HIV (including anything entirely due to a sexual partner you are/were with) - would you consider that you have been at high risk of HIV?	Very high; somewhat high; somewhat low; very low	
Section 4: Motivators of HIV testing			
	When offered an HIVST by your partner, did any of the following encourage you to test		
M_HIV_Test_IU 1	I tested because it was convenient and easy for me to self-test than to test at the clinic	No; Yes	0; 1
M_HIV_Test_IU 2	I have never had an HIV-test and wanted to learn my status	No; Yes	0; 1
M_HIV_Test_IU 3	I had never used an HIV self-test and wanted to use one	No; Yes	0; 1
M_HIV_Test_IU 4	I recently tested HIV negative and wanted to re-check	No; Yes	0; 1
M_HIV_Test_IU 5	I recently tested HIV positive and wanted to confirm my status		
M_HIV_Test_IU 8	I was sick and suspected it was because of HIV	No; Yes	0; 1
M_HIV_Test_IU 9	HIV is very common in this community so I thought I might be positive	No; Yes	0; 1
M_HIV_Test_IU 10	I thought my current/past sexual behaviour put me at high risk of getting HIV	No; Yes	0; 1

M_HIV_Test_IU 11	Many people I know have tested for HIV so I wanted to test as well	No; Yes	0; 1

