Drugs_2	In the last 12 months, have you used drugs recreationally?	No; Yes	0; 1
Drugs_3	In the last 12 months, which drugs have you used?	Cannabis/Marijuana; Cocaine/Crack; Khat/Miraa; Ecstasy/Disco biscuit; Heroin; Amphetamine/Speeed; Tik; Nyamba (any)	; 2; 3; 4; 5; 6; 7

		drug mixed with ART and smoked); Glue/solvents/petrol sniffing; Other (Specify)	
Section 6: Linkage to HIV care (Only for those who self-test HIV positive)			
Link_HIV_Care 1	After self-testing HIV positive, did you go to the clinic to confirm your results?	No; Yes	0; 1
Link_HIV_Care 2	What was result of your confirmatory test?	Negative; Positive; I don't know; Refuse to respond	1; 2; 3; 4
Link_HIV_Care 3	After confirming your HIV-positive status, did you register at the clinic for HIV services?	No; Yes	0; 1
Link_HIV_Care 4	If yes, what date did you register for HIV care?	MMYYYY	[01011900 if UNKNOWN]
Link_HIV_Care 5	At which clinic did you register for ART care?	At the clinic in my community; At another clinic outside my community; at a private clinic	1; 2; 3
Link_HIV_Care 6	At the clinic, were you given the result of a CD4 cell count test?	No; Yes; Don't know/Refused	0;1; -1
Link_HIV_Care 7	If yes, do you know the result of your last CD4 cell count test?	No; Yes	0; 1
Link_HIV_Care 8	What was the CD4 count result?		
Link_HIV_Care 9	Why did you not register at a clinic for HIV care?	Not ready; clinic too far from home;	1; 2; 3
Link_HIV_Care 10	Have you started taking ART treatment?	No; Yes	0; 1

Link_HIV_Care 11	When did you start taking ART?	DDMMYYYY	
Link_HIV_Care 12	Do you know people who are taking ART?	No; Yes	0; 1
Link_HIV_Care 8 1	Who was it you knew, who had been on ART? Please choose all that apply from:	Sexual partner; Household member(s) (not including sexual partner); friend(s)/neighbour(s)/colleague(s); other	1; 2; 3; 4
Link_HIV_Care 9	Have you disclosed your HIV status to anyone, except to me for the purpose of this study?	No; Yes	0; 1 If No skip to Link_HIV_Care 5
Link_HIV_Care 10	To whom did you disclose your HIV status?	husband/wife /Sexual partner; Family Member; Friend/neighbour/colleague; Religious leader/; Health care; Other	1; 2; 3; 4; 5
Link_HIV_Care 11	What are the reasons why you did not register for ART care?	The clinic is too far; The hours of the clinic don't suit me; I did not have transport to go the clinic; I'm not interested in ART	1; 2; 3; 4;

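### The linkage definition does not separate HIV care begun after the kit from ART care that already existed; exposure is greatest in the index-reported outcome and the ANC cohort

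*Protocol*

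**What the plan says.** **Definition.** Section 7.3 has linkage to care "defined as accessing confirmatory testing services or attending an HIV care clinic for HIV-positive individuals", with VMMC as the route for HIV-negative men. The denominator is those linked "among those who reported use of the HIVST". Prior diagnosis and prior ART are not conditions.

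**Windows.** Objective 11 and secondary outcome 3 (section 4.3.2) run about 3 months from distribution. Secondary outcome 2, reported by the index patient, runs 1 month from distribution.

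**Source.** Section 7.3 takes linkage from the intended users. The second paragraph of section 7.4 says linkage will rest primarily on the index individual's report, with intended users added where they consent.

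**Who is offered kits.** Table 1 restricts model 5 to index patients who report a discordant relationship, a partner of unknown status, or a negative partner who wishes to re-test. For model 4 it says only that "HIVST for secondary distribution will be offered to women attending ANC for their primary partners".

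**Questions asked (Appendix 3).** The index follow-up form asks whether the partner went to a facility for HIV care (Use_HIVST 11) and "Is your partner currently in ART care" (coded Use_HIVST 122). Neither refers to the kit or to a date. The intended-user form asks about confirmatory testing after the positive self-test, then about registration after confirmation with its date, then "Have you started taking ART treatment" and the ART start date.

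**The concern.** The study wants to know whether these models reach people, men especially, who did not know their status, and bring them into services (section 1.4). A linkage proportion answers that only if it counts care that followed the kit. A man already on ART who uses a kit and collects his drugs as usual meets the section 7.3 wording and the HIV care element of secondary outcome 3b. In index report he can also appear as in care under secondary outcome 2.

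The forms foresee known-positive kit users. One listed motive for using the kit is "I recently tested HIV positive and wanted to confirm my status", and the ANC exit interview lets a woman report her partner as positive before the questions on the offer and its acceptance.

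Two results would be affected: the linkage proportion itself, and the linkage costs in section 4.4.2, which multiply utilisation reported in the cohort by unit costs. Visits that would have happened anyway could be costed as kit-generated.

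**Working it through.** The protocol states no linkage figure to reproduce, so the check is textual first, then an illustration of size.

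**1. Do the windows exclude existing care?** No. They date the visit, not the start of care. The ART costing questionnaire in Appendix 5 offers monthly, bi-monthly and quarterly as drug-collection intervals. A monthly collection would ordinarily fall inside both windows, and a quarterly one inside 3 months.

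**2. Do the questions exclude it?**

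| Question | Tied to the kit or self-test? |
|---|---|
| Intended user: confirmatory test | Yes, after the positive self-test |
| Intended user: registered for HIV services | Yes, after confirmation; date asked |
| Intended user: started ART | Not in its wording; start date asked |
| Index: partner sought confirmation | Yes, of the self-test result |
| Index: partner went for HIV care | No |
| Index: partner currently in ART care | No |

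The intended-user form records the last HIV result before the kit and the ART start date, but no rule in sections 4.3.2, 5, 7.3 or 7.4 uses them to set aside existing patients. For VMMC the same form does have a separate answer for men already circumcised; HIV care has no equivalent.

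**3. Size among HIV-positive kit users.** Let f be the share already in ART care, all assumed to be counted as linked, and L the true linkage among the rest. Both are assumptions.

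Apparent linkage = f + (1 − f)L, so inflation = f(1 − L).

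| | f = 5% | f = 10% | f = 20% | f = 30% |
|---|---|---|---|---|
| L = 30% | 33.5% (+3.5) | 37% (+7) | 44% (+14) | 51% (+21) |
| L = 50% | 52.5% (+2.5) | 55% (+5) | 60% (+10) | 65% (+15) |
| L = 70% | 71.5% (+1.5) | 73% (+3) | 76% (+6) | 79% (+9) |

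The range is 1.5 to 21 percentage points, and zero if no kit user was already in care.

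**4. Size on the protocol's denominator.** Section 7.3 divides by all kit users. Let p be the HIV-positive share of kit users and C the linkage among all users not already in care. Existing patients are then a share pf of all users, so

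Apparent = pf + (1 − pf)C, and inflation = pf(1− C), which cannot exceed pf.

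The documents do not give p for partners. Assuming 5–20%, the ceiling pf runs from 0.05 × 0.05 = 0.25 points to 0.20 × 0.30 = 6 points.

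**The case against.** **The protocol does set a start point.** This stands. A reader who sees only the parenthesis in section 7.3 might infer that linkage has none. Objective 11 and secondary outcomes 2 and 3 start at distribution, and the main intended-user questions follow the self-test and confirmation. What survives is narrower: a window from distribution does not tell new care from continuing care.

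**Known-positive partners may drop out before the denominator.** This stands in part. On the index form "my partner already knows his/her HIV positive status" is a reason for not handing over the kit, and the intended-user form has a similar reason for not using it. Such men are not counted. It argues for a modest f, not for f = 0.

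**National figures do not measure the bias.** This also stands. Section 1.1 reports that "In 2016 in Zambia, 70% of women and 63% of men knew their HIV-positive status", with about 85% of those diagnosed on ART, so 0.63 × 0.85 = 54% of HIV-positive men were on ART. A reader might infer that true linkage of 30% would be reported as 0.536 + 0.464 × 0.30 = 68%. That figure treats HIV-positive men in general as if they were HIV-positive kit users, and it is not on the all-user denominator that section 7.3 reports.

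**Cohort comparison.** A reader might infer that the difference between models 4 and 5 spoils a comparison. None is planned: section 7.3 analyses the cohorts separately, and section 5.4 calls the linkage results descriptive.

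**This is SAP detail.** This does not stand. The protocol fixes the definition in section 7.3 and prints the index questions. An analysis plan could use dates the intended user gave; it cannot supply a date the index patient was never asked for.

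**Conclusion.** The point holds in limited form. As written, the plan can count existing ART care as linkage after the kit, and no rule separates the two. Exposure is greatest for index-reported secondary outcome 2 and in the ANC cohort, where partner status is not restricted. It is smaller where the intended user answers for himself. Section 7.4 enlarges it by making index report the primary source, contrary to section 7.3.

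The figures of 1.5–21 points among HIV-positive users, and at most 0.25–6 points over all kit users, rest on assumed values of f, L and p and on every existing patient being counted as linked. They show scale and are not estimates. The primary outcome (partner's use of the kit) and the sample size are untouched. Linkage is descriptive, but the reported proportion is itself the result, so the correction is worth making.

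**What to change.** 1. In section 7.3, and for secondary outcomes 2 and 3b, count linkage to HIV care only as confirmatory testing, first registration, ART start or re-entry to care on or after the date the kit was received.
2. Tabulate kit users already in HIV care or on ART before the kit separately, outside numerator and denominator, using the registration and ART start dates on the intended-user form. Keep previously diagnosed users who were not in care in the denominator: their return is real linkage, so excluding everyone with a prior positive result would be wrong. The form has no question on interrupted care, so one added question on whether the respondent was in HIV care when the kit arrived would be needed to recognise re-entry.
3. Add the words *since receiving the kit* to the two index questions on HIV care and current ART. Where the partner was reported positive at the exit interview, do not count current ART care as linkage unless care began after the kit.
4. Reconcile sections 7.3 and 7.4 on which source is primary for linkage.

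The cost is a few lines of protocol text and small questionnaire edits; most of the data are already collected. The index wording must change before the interviews, since it cannot be repaired afterwards. The price is a slightly smaller denominator and a less favourable linkage figure.
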